7.9.2 Secondary Objective #1 – VAS at the 6-Month Visit

To demonstrate pain intensity scores (VAS) at the 6-Month Visit is non-inferior to VAS at Baseline.

7.9.2.1 Hypothesis

The mean change in pain intensity using VAS from Baseline to the 6-Month Visit is not worse than 0 by more than 10 points.

$$H_0: \mu \geq 0 + |M|$$

$$H_A: \mu < 0 + |M|$$

Where μ is the mean change in VAS from Baseline to the 6-Month Visit and $|M|$ is the absolute value of non-inferiority margin of 10.

7.9.2.2 Experimental Design

The measurement of pain intensity using VAS is described in Section 5.2.1.1. The change in VAS is calculated using VAS at the 6-Month Visit minus VAS at the Baseline Visit. A negative change is an improvement.

7.9.2.3 Analysis Methods

The change in VAS as well as VAS at both Baseline and the 6-Month Visit will be summarized using descriptive statistics, (e.g., mean, standard deviations, etc.). The non-inferiority null hypothesis will be tested using a one-sided 0.025 alpha level one sample t-test. The upper bound of the 95% CI of the mean change must be less than 10. If non-inferiority is met, a two-sided 0.05 alpha level t-test for superiority (vs. 0 change from Baseline) will be performed. If the distribution of the change in VAS doesn't meet normality assumption (Shapiro-Wilk test), an appropriate non-parametric analysis such as Wilcoxon signed rank test will be performed. The primary analysis will use all the implanted subjects who maintain morphine monotherapy and provide data at both Baseline and 6-Month Visits.

Two sensitivity analyses will be performed, one will include subjects who provide data (completers) and one will include all implanted subjects. The sensitivity analysis of all implanted subjects will be performed using MI method for missing data at the Baseline and the 6-Month Visits. For missing VAS at

the scheduled 6-Month Visit, if an Unscheduled Visit occurred within the 6-Month Visit window, and the VAS is collected at the Unscheduled Visit, the VAS from the Unscheduled Visit will be used in the analysis of the 6-Month Visit. Otherwise, the missing VAS will be imputed using MI. Prior to the use of MI, the distributions of the continuous variables will be assessed for normality and the need for transformation if they are not normally distributed. The model variables in MI may include the following when deemed appropriate: study site, subject age, gender, primary diagnosis, VAS at Baseline, 1-Month Visit, 3-Month Visit. The fully conditional specification (FCS) method with 10 burn-in iterations within SAS and 10 repetitions ($M = 10$) will be used for imputation. Constraints will be set so that the imputed VAS are restricted to values ranging from 0-100. If the MI procedure is unable to successfully impute values within that range, the constraints will be applied after imputation, such that any values less than 0 will be set to 0, and any values greater than 100 will be set to 100. Following imputation, the objective will be evaluated using MI analysis method in SAS.

In addition, percentage of change in VAS will be calculated using change in VAS divided by VAS at Baseline. A negative percentage of change in VAS is a percentage of reduction in VAS, thus an improvement. The percentage of change in VAS will be summarized using descriptive statistics, (e.g., median and inter-quartile range, etc.). If a subject has VAS equal to 0 at both the Baseline and the 6-Month Visit, the percentage of change will be 0%. If a subject has VAS equal to 0 at the Baseline visit, and non-zero at the 6-Month Visit, this subject will be excluded from summary of percentage of change in VAS.

If more than 10% of the 6-Month Visits within the Per-protocol Analysis Set are conducted remotely, an additional sensitivity analysis of the Per-protocol Analysis Set will be performed as described in Section 7.4.1. Changes in VAS will be characterized without statistical testing for this analysis.

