9.3 Inclusion Criteria

A potential subject may be included for participation in the study if the subject has/is:

1. Willing and able to provide a signed and dated (Medtronic and Institutional Review Board (IRB) approved) Informed Consent Form (ICF) and Health Insurance Portability and Accountability Act (HIPAA) Authorization Form prior to any study procedures being performed
2. A candidate per labeling for the IDDS
3. A diagnosis of chronic, intractable, non-malignant primary back pain with or without leg pain, treatable with the IDDS
4. Current daily systemic opioid dose of >0 and ≤ 120 Morphine Milligram Equivalents (MME)
5. A Visual Analogue Scale (VAS) of ≥50 mm for pain intensity at the Baseline Visit and/or a Numerical Opioid Side Effect (NOSE) Assessment Tool ≥40 for intolerable side effects at the Baseline Visit
6. Psychological evaluation or investigator assessment of patient psychological suitability for study participation
7. Has an MRI or CT prior to enrollment verifying patent spinal canal and no clinical change in status since last imaging
8. At least 18 years old at time of enrollment
9. Willing and able to attend visits and comply with the study protocol
10. Male or non-pregnant, non-lactating female. Females must be post-menopausal or surgically sterile; or be utilizing a medically acceptable form of birth control (i.e. a hormonal contraceptive, intra-uterine device, diaphragm with spermicide, or condom with spermicide) for the duration of the study

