10.2 Baseline Visit

Subjects are considered enrolled at the time the study-specific informed consent/HIPAA form is signed. At the Baseline Visit, the Medtronic and site Institutional Review Board (IRB) approved informed consent/HIPAA form will be reviewed with the potential subject. If the subject agrees to participate, they will be consented and assessed for eligibility to the study-specific inclusion and exclusion criteria. Each subject must meet all the inclusion criteria and none of the exclusion criteria to be eligible to participate in this study. No study-related procedures or testing will be conducted prior to completing the consenting process of a subject.

Subjects will be asked to complete the VAS for pain intensity and the NOSE assessment tool. Site personnel will confirm the subject's VAS score ≥ 50 mm or the subject's NOSE score ≥ 40 to be eligible to continue in the study. Female subjects of child-bearing potential (not post-menopausal or surgically sterile) must be administered a urine pregnancy test to confirm they are not pregnant at this visit. A subject who has a positive urine pregnancy test will be exited from the study according to Section 10.10. In addition, site personnel must confirm the drug testing results are negative for cannabinoids and illicit drugs for all subjects. If subjects meet all the eligibility criteria, their chronic back (and leg, if applicable) pain history and surgical history will be collected and the study investigator will discuss the process for weaning off systemic opioids with the subject.

Systemic Opioid Weaning and Holiday

Investigators should begin weaning the subject off their systemic opioids on the day of their Baseline Visit (i.e., enrolment date). The method of the opioid weaning process is at the investigator's discretion, but must be completed within the following constraints:

- Total duration (Baseline to Implant \leq 5 months)
- Systemic opioid dose of \leq 60 MME before IT trial
- Minimum opioid holiday of at least 7 days prior to IT Therapy Initiation

If a subject has been enrolled in the study and is determined to be ineligible during the Baseline Visit, or they choose to withdraw early, the subject will be exited according to Section 10.10.

Data Collection Requirements for the Baseline Visit:

- ICF/HIPAA
- Inclusion/exclusion criteria
- VAS
- NOSE
- Demographics
- Back (and leg, if present) pain history/surgical history
- Adjunctive pain management therapies utilized

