Approximately 100 subjects will be enrolled into the study to get a minimum of 67 implanted subjects and at least 50 evaluable subjects at the 6-Month Visit. The sample size of 50 evaluable subjects was chosen to assure acceptable levels of precision for estimation of the primary objective of Clinical Success and provide adequate power to test the secondary objective related to pain score.

There were no available data in the target population on the primary objective of Clinical Success, nor on the secondary objective of opioid-related side effects score. The secondary objective of pain intensity score is used for sample size calculation. It is hypothesized that the pain intensity score of VAS at the 6-Month Visit is non-inferior to those at Baseline using a non-inferiority approach.

The PASS 11 Non-Inferiority Tests for One Mean was used to calculate the power for pain intensity of VAS with the following assumptions: Sample size = 50, Alpha = 0.025, Non-Inferiority Margin = 1, True Difference = 0, Standard Deviation = 1.9, with Higher Means are Worse (one-sided) t-test. A sample size of 50 would achieve 95% power with the above assumptions. This power calculation was performed using a pain scale of 0-10; however, the power calculation is identical to one with a non-inferiority margin of 10 and assuming a standard deviation of 19 on a VAS pain scale of 0-100.

The non-inferiority margin of 10 points was chosen based on a review of pain study literature. Non-inferiority margins between 1 and 1.5 were reported for pain scales of 0-10, including one study in a similar population of chronic non-malignant pain subjects comparing 2 oral opioids that utilized a margin of 1.¹ The estimated actual difference was assumed to be 0 because the goal is to achieve same or better pain control as compared to Baseline.

The non-inferiority margin of 1 on a pain scale of 0-10 is equivalent to a non-inferiority margin of 10 on a VAS pain scale of 0-100.

A 33% attrition between enrollment and subject implant is assumed and a 25% attrition between Implant and the 6-Month Visit is assumed. To achieve at least 50 evaluable subjects at the 6-Month Visit, a minimum of 67 subjects are required to be implanted and approximately 100 subjects to be enrolled.

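### The Baseline reading that admits a subject is also the comparator for change, so a VAS superiority result (or non-inferiority near the margin) cannot be read as a change in underlying pain

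*SAP*

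**What the plan says.** - **Entry.** Protocol 9.3, item 5, admits on "A Visual Analogue Scale (VAS) of ≥50 mm for pain intensity at the Baseline Visit and/or" a NOSE score of at least 40. Protocol 10.2 ties this to the Baseline Visit: "Site personnel will confirm the subject's VAS score ≥ 50 mm or the subject's NOSE score ≥ 40 to be eligible".
- **Comparator.** SAP 7.9.2.2: "The change in VAS is calculated using VAS at the 6-Month Visit minus VAS at the Baseline Visit". It is the same single reading.
- **Parameter.** SAP 7.9.2.1 defines the tested parameter, which "is the mean change in VAS from Baseline to the 6-Month Visit".
- **Tests.** SAP 7.9.2.3: "The non-inferiority null hypothesis will be tested using a one-sided 0.025 alpha level one sample t-test", against a margin of 10. It continues: "If non-inferiority is met, a two-sided 0.05 alpha level t-test for superiority (vs. 0 change from Baseline) will be performed". Protocol 14.4.1 has the same pair of tests.
- **Variability.** SAP Section 6 plans for 50 evaluable subjects, "assuming a standard deviation of 19 on a VAS pain scale of 0-100".
- **What is absent.** The bias-control measures listed in Protocol Section 6 do not mention selection on the Baseline score. The sensitivity analyses (completers, multiple imputation, remote visits) all keep that same Baseline.

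**The concern.** The VAS is one mark for average pain over 24 hours (SAP 5.2.1.1), so some of any reading is day-to-day variation. A subject who qualifies because the Baseline mark was high will, on average, mark lower later even if nothing has changed. Subtracting the qualifying reading puts that fall into the change score, and without a control group it cannot be separated from an effect of the route change.

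The VAS tests are the only hypothesis tests in the study (SAP 7.5). The stated purpose is to assess pain control after the route change (SAP 5.1), and the assumed true difference of 0 is justified by a goal of the same or better pain control (SAP Section 6). A reader will therefore take a significant result as evidence about underlying pain. The drift favours the therapy, so superiority could be reported with no change in underlying pain, and non-inferiority could be met when underlying pain is worse by about the margin.

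**Working it through.** **1. The plan's own figure.** With n = 50, margin 10, SD 19, true difference 0 and one-sided alpha 0.025, the noncentrality is √50 × 10/19 = 3.72. Power = P(T with 49 df and that noncentrality exceeds 2.01) = 0.954. The stated 95% reproduces.

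**2. Test size for the hypothesis as written.** Subjects were simulated with entry on VAS alone (candidate mean 60, test-retest correlation 0.6), with the mean change in the selected subjects fixed at exactly 0 or exactly 10. Rejection rates were 0.050 (two-sided, against 0) and 0.024 (one-sided, against 10). Nominal size holds.

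**3. Expected drift with no true change, entry on VAS alone.** Let m be the candidate mean and ρ the test-retest correlation (both assumed), with the SD of change before selection fixed at 19.

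- SD of VAS = 19/√(2(1−ρ)), and a = (50 − m)/SD.
- Drift = −(1−ρ) × SD × φ(a)/(1−Φ(a)).
- For m = 60 and ρ = 0.6: SD = 21.24, a = −0.471, φ/(1−Φ) = 0.357/0.681 = 0.524, so drift = −0.4 × 21.24 × 0.524, about −4.5 mm.

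**4. The actual either/or rule.** Same model, with NOSE mean 35, NOSE SD 18 and VAS-NOSE correlation 0.2 (all assumed), n = 50, 20,000 simulated tests per cell. Each cell gives mean VAS change in mm, then the share of trials declaring improvement (nominal 2.5%).

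| Candidate VAS mean | ρ = 0.4 | ρ = 0.6 | ρ = 0.8 |
|---|---|---|---|
| 50 | −4.4; 39% | −3.6; 27% | −2.5; 15% |
| 60 | −3.2; 23% | −2.8; 18% | −2.1; 12% |
| 70 | −1.7; 9% | −1.8; 10% | −1.7; 9% |

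In the same cells, with a true worsening of exactly 10 mm, the observed mean change is +5.6 to +8.4 and non-inferiority is declared in 9% to 37% of trials.

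**5. A wider set of assumptions.** Scores were limited to 0–100, with candidate VAS mean 55–70, between-subject SD 12–18, SD of change 12 or 19, and candidate NOSE mean 15–35. Mean VAS change with no effect is about −0.6 to −6 mm, and improvement is declared in about 5% to 60% of trials. The low end comes from SD of change 12 with a VAS mean well above 50. The high end comes from SD 19 with a mean near 50 and few subjects at NOSE 40 or above.

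**6. From drift to rejection rate.** With SD 19 and n = 50, the chance of declaring improvement is P(T with 49 df and noncentrality √50 × drift/19 exceeds 2.01).

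| Drift (mm) | 1 | 2 | 3 | 4 | 5 | 6 |
|---|---|---|---|---|---|---|
| Improvement declared | 5.5% | 10.9% | 19.3% | 30.8% | 44.6% | 59.1% |

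**7. Other planned results.** Drift in the all-subject NOSE mean is about 0 to −2.6 points. Clinical Success with no true change is 29% to 38% with the entry rule and 28% to 31% without it.

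**8. Subsets whose entry did not depend on the score analysed.** Everyone with Baseline NOSE of at least 40 enters whatever the VAS. VAS drift in that subset is 0.0 ± 0.1 mm if same-day VAS and NOSE errors are independent. If those errors correlate 0.3, it is −1.2 to −4.6 mm, in some cells more than in the full set.

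**The case against.** A reader might infer that the two t-tests fail to hold their stated alpha. The documents do not support that. SAP 7.9.2.1 defines the parameter as the mean observed change, which in the enrolled population already contains the regression, and step 2 shows nominal size for it. The 5% to 60% figures answer a different null, no change in underlying pain. The fault lies in what a rejection can be taken to mean.

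A reader might also infer that the NOSE result is inflated to the same degree. In subjects with Baseline NOSE of 40 or more the fall can be large, but SAP 7.9.3.3 summarises all per-protocol subjects, without a test. Those below 40 drift the other way, and the net effect is small.

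Further points on the other side stand:

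- The documents give no VAS reliability, no candidate mean or SD, and no count of subjects entering on NOSE alone. The upper figures treat the whole SD of change as measurement variation and none of it as varying response. The ranges are illustrations, not bounds.
- False non-inferiority at these rates needs a true worsening of about 10 mm.
- The primary objective is descriptive and little affected.
- All 93 subjects are enrolled, so a second baseline cannot be added. VAS scores at the IT Trial and IT Therapy Initiation fall during or after weaning and are not a clean substitute.

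These points limit the size and the choice of remedy. They do not remove the problem: every cell examined drifted in the therapy's favour, and no planned analysis would show it.

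**Conclusion.** The point holds as one of interpretation. The same reading admits and is the comparator, and nothing in either document allows for it. Significant superiority, or non-inferiority reached near the margin, cannot by itself be read as a change in underlying pain after the route change. With no effect, the assumed inputs in step 5 give a mean VAS change of about −0.6 to −6 mm, and improvement declared in about 5% to 60% of trials against 2.5%. The drift shrinks when typical VAS lies well above 50, when readings vary less from day to day, or when more subjects enter on NOSE alone. The effect on the planned NOSE mean is about 0 to −3 points.

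A large observed improvement would be safe. At SD 19 and n = 50 the half-width of the 95% interval is 2.01 × 19/√50 = 5.40 mm. After 6 mm is added back, superiority survives if the observed mean change is below −(6 + 5.40) = −11.40 mm, and non-inferiority survives if it is below 10 − 6 − 5.40 = −1.40 mm. The change is worth making because it is cheap and bears on the study's only hypothesis tests.

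**What to change.** In SAP 7.9.2.3:

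- **(a) Tipping point.** Add an assumed regression to the mean of 1 to 6 mm to the mean change. Report the smallest value at which superiority is lost and the smallest at which the upper 95% limit reaches 10. With observed mean d and half-width h, these are −(d + h) and 10 − (d + h). If the non-parametric route is used, add the constant to each subject's change and repeat that test.
- **(b) Wording.** Describe the superiority result as within-subject change from Baseline. Do not present it as a therapy effect unless it survives the 1 to 6 mm range. State the shared reading as a limitation.
- **(c) Support only.** Report VAS change in all subjects with Baseline NOSE of at least 40 and, in 7.9.3.3, NOSE change in all subjects with Baseline VAS of at least 50. State that these are free of the selection only if same-day VAS and NOSE errors are independent, and that the first subset may be small: at a candidate NOSE mean of 15 it is 8–17% of entrants, or 4 to 9 of 50.

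I would not rely on a truncated-normal correction confined to subjects with NOSE below 40. It leaves untouched any drift in those at 40 or above. It also needs a candidate mean and SD that the truncated sample does not directly supply, and estimating its variance from 3- and 6-Month scores would use on-treatment readings taken while dose changes are allowed.

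The cost is SAP wording and one or two tables from data already collected. The superiority claim may weaken.

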14.4.1 Secondary Objective #1 – VAS Pain Intensity at the 6-Month Visit

To demonstrate pain intensity scores (VAS) at the 6-Month Visit is non-inferior to VAS at Baseline.

Hypothesis

The mean change in pain intensity using VAS from Baseline to the 6-Month Visit is not worse than 0 by more than 10 points.

$$H_0: \mu \geq 0 + |M|$$

$$H_A: \mu < 0 + |M|$$

Where μ is the mean change in VAS from Baseline to the 6-Month Visit and $|M|$ is the absolute value of non-inferiority margin of 10.

Experimental Design

The measurements of pain intensity using VAS is described in Section 10.17.1. The change in VAS is calculated using VAS at the 6-Month Visit minus VAS at the Baseline Visit. A negative change is an improvement.

Analysis Methods

The change in VAS as well as VAS at both Baseline and the 6-Month Visit will be summarized using descriptive statistics, (e.g., mean, standard deviations, etc.). The non-inferiority null hypothesis will be tested using a one-sided 0.025 alpha level one sample t-test. The upper bound of the 95% CI of the mean change must be less than 10. If non-inferiority is met, a two-sided 0.05 alpha level t-test for superiority (vs. 0 change from Baseline) will be performed. If the distribution of the change in VAS doesn't meet normality assumption, an appropriate non-parametric analysis will be performed. The

primary analysis will use all the implanted subjects who maintain morphine monotherapy and provide data at both Baseline and 6-Month Visits.

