The 33% attrition between enrollment and subject implant accounts for the subjects who don't meet inclusion and/or exclusion criteria, those who can't follow the weaning process to eliminate systemic opioids, those who don't have a successful IT trial, those who have adverse events that can no longer be followed in the study, withdrawals, and lost-to-follow-up, etc. The attrition between implant and the 6-Month Visit is conservatively set at 25% to potentially account for the subjects who have adverse events that can no longer be followed in the study, withdrawals, are lost-to-follow-up, or subjects who can't be effectively managed on morphine monotherapy.

7. Statistical Methods

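### The VAS non-inferiority and superiority decisions rest on the per-protocol set; for the implanted population the false-positive rate can exceed 2.5% if excluded subjects do worse

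*SAP*

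**What the plan says.** The VAS change is "tested using a one-sided 0.025 alpha level one sample t-test". The criterion is "The upper bound of the 95% CI of the mean change must be less than 10", and then "If non-inferiority is met, a two-sided 0.05 alpha level t-test for superiority (vs. 0 change from Baseline) will be performed". For the population, SAP 7.9.2.3 states: "The primary analysis will use all the implanted subjects who maintain morphine monotherapy and provide data at both Baseline and 6-Month Visits". Protocol 14.4.1 gives the same rule and the same set. SAP 7.5 says that this objective holds the study's only hypothesis testing.

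Two sensitivity analyses follow in the same SAP section: one in completers, one in all implanted subjects with MI. SAP 7.1.3 calls both sets supporting. Neither document requires them to meet the margin or says what happens if they disagree with the per-protocol result.

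The objective (SAP 4.2) and the definition of mu (SAP 7.9.2.1) refer to VAS at 6 Months against Baseline, with no limit to subjects who maintain monotherapy. SAP 6 plans a 25% loss after implant, "conservatively set at 25% to potentially account for the subjects who have adverse events that can no longer be followed in the study". The same sentence adds withdrawals, loss to follow-up and subjects whom morphine monotherapy could not manage.

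**The concern.** Membership of the per-protocol set depends on events after implant, and some of the reasons for leaving it are treatment failures by description. If the subjects who leave have more pain at 6 Months than those who stay, the per-protocol mean is better than the mean for everyone implanted, and both tests lean towards the favourable answer.

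Some of the scores set aside may well have been collected. Protocol 10.7 treats loss of monotherapy as a deviation to be recorded, and Protocol 10.21 asks sites to obtain the 6-Month assessments from subjects who leave early.

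This objective drives the sample size and is the only one worded as a demonstration. What is at stake is a declaration of non-inferiority or superiority that is read as applying to implanted patients when it may hold only for those in whom the therapy could be continued.

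**Working it through.** **Inputs.** SAP 6: "Sample size = 50, Alpha = 0.025, Non-Inferiority Margin = 1, True Difference = 0, Standard Deviation = 1.9" on the 0-10 scale, equivalent to margin 10 and SD 19 on 0-100; 67 implanted; 25% post-implant loss, so 50 analysed and 17 excluded. SAP 7.9.2.3: one-sided 0.025 one-sample t-test. *Assumption, not in the documents:* excluded subjects average d mm worse on VAS change than retained subjects, with SD 19 in both groups.

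**The plan's own figure.** Noncentrality = 10 × √50 / 19 = 3.72, with 49 df and critical value 2.010. Power is 95.4%, so the stated 95% reproduces.

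**False non-inferiority for the implanted population.** Fix the all-implanted mean change at the boundary of 10. With excluded fraction f = 17/67, the retained mean is 10 − f·d. The per-protocol test then rejects with the power of a t-test at n = 50 and noncentrality f·d·√50/19.

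| d (mm) | retained mean | noncentrality | false-positive rate |
|---|---|---|---|
| 0 | 10.00 | 0 | 2.5% |
| 5 | 8.73 | 0.47 | 6.7% |
| 10 | 7.46 | 0.94 | 15.1% |
| 15 | 6.19 | 1.42 | 28.4% |
| 20 | 4.93 | 1.89 | 45.7% |

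With f = 0.10 and n = 60, the rate is 3.9% at d = 5 (noncentrality 0.5 × √60 / 19 = 0.20) and 6.0% at d = 10 (0.41).

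**False superiority.** Fix the all-implanted mean at 0. The retained mean is −f·d, so the chance of a false finding of improvement has the same values as the table. The non-inferiority gate gives no protection here: an upper bound below 0 is always below 10.

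**How a conclusion could flip** (SD 19 in each group, mean and variance pooled over 67):
- Superiority: a per-protocol mean of −6 gives p = 0.030. With the 17 excluded at 0, the all-implanted mean is (50 × −6 + 17 × 0)/67 = −4.5 and p = 0.059.
- Non-inferiority: a per-protocol mean of +4 has upper bound 4 + 2.010 × 19/√50 = 9.4, which meets the margin. With the excluded at +15, the all-implanted mean is (50 × 4 + 17 × 15)/67 = 6.8 and the upper bound is 11.5, which does not.

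**Does requiring both sets help?** If all 67 outcomes are observed, the all-implanted test at the boundary rejects in 2.4% of simulated trials at d = 0 and 2.1% at d = 10. If all 17 are missing and are imputed from one earlier VAS change (assumed correlation rho with the 6-Month change), the both-sets rule at d = 10 still gives about 13%, 9% and 7% at rho = 0, 0.5 and 0.7. If 8 of the 17 are observed and rho = 0.5, it gives about 5%.

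**The case against.** The strongest reply is that the tests are valid as specified. Both documents consistently name the analysed set, and for subjects who maintain monotherapy and have both visits the t-test holds its 2.5%. That stands. A reader might infer that the plan fails to control its error rate; the documents do not support this. The excess appears only when the conclusion is carried to implanted subjects as a whole. What remains is that neither the objective nor mu carries the restriction, so nothing in the plan stops that extension.

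A reader might also infer that the plan ignores the excluded subjects. It does not. The completer analysis brings back monotherapy failures who have 6-Month data, and the MI analysis covers everyone implanted, so a discordant result would be visible. It would not change either declaration.

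The size is open to challenge too. The gap is assumed, and the 25% is described as conservative. It includes withdrawals and loss to follow-up, and SAP 7.1.1 also expects discontinuations from COVID-19 and a pump supply shortage, which need not relate to pain. Subjects moved to other drugs could even report less pain. All of this stands, and it is why a range is given.

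Finally, per-protocol analysis is customary for non-inferiority. The usual reason is that non-adherence can dilute a difference between arms. This study has one arm, so that reason does not carry over, and it gives no support to a per-protocol superiority test.

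**Conclusion.** The point holds in a limited form. Both VAS decisions are taken on a set selected by post-implant outcome, the planned wider analyses have no say in them, and the stated target is broader than the set. For the implanted population, the one-sided false-positive rate runs from 2.5% with no gap to 6.7% at 5 mm and 15.1% at 10 mm when 17 of 67 are excluded, and is 3.9% and 6.0% at the same gaps when about 10% are. These figures rest on an assumed gap, SD 19 and normal data. The larger table values need a gap of 15 to 20 mm averaged over all 17 excluded subjects, and nothing in the documents shows that. The rate can be raised; it cannot be said that it will be.

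**What to change.** In SAP 7.9.2.3:

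1. Declare non-inferiority only if the upper 95% bound is below 10 in both the Per-protocol and the Implanted Analysis Sets. In the Implanted set, keep every observed 6-Month score, including those after loss of monotherapy, and impute only the rest.
2. Base the superiority test on the Implanted Analysis Set, with the per-protocol result supportive.
3. If neither change is made, word any conclusion as applying only to subjects who maintained monotherapy through 6 Months.

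Protocol 14.4.1 carries the same rule, so record the change in SAP 7.11 and in the clinical study report.

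The cost is wording and some power, since both analyses are already planned. At a per-protocol true change of 0, requiring both sets gives about 95%, 94% and 87% power if excluded subjects are 0, 5 and 10 mm worse, against about 95% on the per-protocol set alone. Those figures treat all 67 outcomes as observed; with imputation power is somewhat lower. The MI model relies on site, age, gender, diagnosis and earlier VAS, and so assumes data are missing at random. The change therefore reduces the bias without removing it, and works best where 6-Month scores are obtained from subjects who leave.
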